1.3. Schedule of Activities (SoA)

Table 1-1 Schedule of Activities – Stage 1

Study Day (Unless otherwise specified, all examinations/procedures for a	Visit 1 Screening	Visit 2 (Baseline)	Visit 3	Visit 4	Visit 5 (Exit) or Early Termination	
timepoint must be performed in the order listed below)	Day -14 to Day -1	Day 1	Day 2	Day 8 (+1)	Day 15 (+2)	Notes
Informed consent	X					
Inclusion and exclusion criteria	X	X				Recheck participant eligibility before randomization and/or first dose of study intervention.
Demographics	X					
Medical, ophthalmic, and surgical history (includes substance usage)	X	X				
Prior or concomitant medication review	←=====				→	
AE review	←=====				-	
Vital signs (RR, height, and weight)	X				X	Height measurement will not be performed at Visit 5 or the Early Termination visit.
Vital signs (blood pressure, pulse rate, and temperature)	X	X	X	X	X	
Physical examination	X				X	
12-lead ECG	X				X	At the Exit visit, ECG will be performed at 0 hour (predose) and 45 ± 15 minutes postdose.
Pregnancy test (WOCBP only)	X	X			X	Serum pregnancy test will be performed at Screening; at all other indicated visits, serum or urine pregnancy test will be performed.
Drugs of abuse screen	X	X				Breathalyzer may be used for alcohol.
Hematology, chemistry, and urinalysis	X				X	Participants will be instructed to fast (ie, water only) for at least 10 hours prior to blood collection for safety laboratory tests.
Serology	X					

			Interv	ention Period		
Study Day (Unless otherwise specified, all examinations/procedures for a	Visit 1 Screening	Visit 2 (Baseline)	Visit 3	Visit 4	Visit 5 (Exit) or Early Termination	
timepoint must be performed in the order listed below)	Day -14 to Day -1	Day 1	Day 2	Day 8 (+1)	Day 15 (+2)	Notes
	X	X				
Manifest refraction	X	X	X	X	X	
Best-corrected visual acuity	X	X	X	X	X	
Slit lamp biomicroscopy	X	X	X	X	X	
	X	X				
	X	X				
Intraocular pressure	X	X	X	X	X	
Dilated fundus exam	X				X	
Randomization		X				
Blood sample collection for PK analysis		X	X	х	X	Blood samples for PK analysis will be collected at Visit 2 at 0 hour (predose) and at Visits 3 and 5 at 0 hour (predose) and 0.5, 1, 2, 4, 8, and 12 hours postdose. In addition, at Visit 4, a sample will be collected at 0 hour (predose) and at 0.5 hours postdose. At Early Termination visit, only a single sample will be collected. For the full blood sample collection schedule, refer to Table 8-12.

			Interv	ention Period		

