Study Day (Unless otherwise specified, all examinations/procedures for a	Visit 1 Screening	Visit 2 (Baseline)	Visit 3	Visit 4	Visit 5 (Exit) or Early Termination	
timepoint must be performed in the order listed below)	Day -14 to Day -1	Day 1	Day 2	Day 8 (+1)	Day 15 (+2)	Notes
Tear sample collection for PK analysis			X	X	X	Tear samples for PK analysis will be collected at Visits 3 and 5 at 0 hour (predose) and 0.5, 2, 4, 8, and 12 hours postdose. In addition, at Visit 4, a sample will be collected at 0.5 hours postdose. Tear samples will be collected from both eyes. For the full tear sample collection schedule, refer to Table 8-14. Tear collection will not be performed at the Early Termination visit.
Administration of study intervention		X	X	X	X	Study interventions will be administered as a single drop to the left eye on Day 1 and as a single drop to both eyes, twice daily (approximately 12 hours apart) for 13 days (Days 2-14), followed by a single dose administration to both eyes on Day 15. The morning dose will be administered by site staff on visit days. Dosing will not be performed at the Early Termination visit.
Drop Tolerability Questionnaire		X	X	X	X	Drop Tolerability Questionnaire must be administered within approximately 5 minutes following morning administration of study intervention. Drop Tolerability Questionnaire will not be administered at the Early Termination visit.
Dispensing of study intervention to participant			X	X		
Collection of used and unused study intervention		DV 1	1:	X	X	

AE = adverse event; ECG = electrocardiogram;

; PK = pharmacokinetic; RR = respiration rate; WOCBP = women of childbearing potential

[figure not shown]

Table 1-2 Schedule of Activities – Stage 2

Study Day						Intouron	tion Period	 			
Unless otherwise specified with a '#', all		it 1 ening	Visit 2		sit 3 eline)	Visit 4	Visit 5	Vis (E:	sit 6 xit)	Early Termination	Notes
examinations/procedures for a timepoint will be		4 days Visit 2	Day -14 (± 2)	Da	ıy 1	Day 14 (± 2)	Day 28 (± 3)		y 42 : 5)	NA	
performed in the order listed below*	Pre- CAE	Post- CAE	NA	Pre- CAE	Post- CAE	NA	NA	Pre- CAE	Post- CAE	NA	
Informed consent	X										
Inclusion and exclusion criteria	X	X		X	X						Recheck participant eligibility before randomization and/or first dose of study intervention
Demographics #	X										
Medical, ophthalmic, and surgical history (includes substance usage) #	Х		X	Х							

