4.4. End of Study Definition

The end of the study is defined as the date of the last visit of the last participant in the study or last scheduled procedure shown in the SoA (Section 1.3) for the last participant in the study.

The Exit visit is defined as the last visit or the last scheduled procedure shown in the SoA for each stage of the study (Section 1.3). A participant is considered to have completed the study if he/she has completed all study visits including the Exit visit. If the participant is discontinued or withdraws from the study before the Exit visit, the last visit before the discontinuation or withdrawal will be considered an Early Termination visit.

5. Study Population

All participants will have DED. In addition, participants enrolled in Stage 2 of this study will have to respond to the CAE challenge with increased signs and symptoms of DED (see Sections 4.1 and 4.2.4 for more details).

Prospective approval of protocol deviations to recruitment and enrollment criteria, also known as protocol waivers or exemptions, is not permitted.

5.1. Stage 1

5.1.1. Inclusion Criteria for Stage 1

Participants are eligible to be included in Stage 1 of the study only if all of the following criteria apply:

1.	Age
1.01	Participant must be ≥ 18 years of age at the time of signing the informed consent
2.	Type of Participant and Disease Characteristics
2.01	Both of the following signs of DED in at least 1 eye at Screening and Baseline visits (the same eye does not need to qualify at both visits):
	 Total corneal fluorescein staining score ≥ 2 and ≤ 9 based on the NEI grading scale, with no score > 2 in any 1 region
	• Schirmer test with topical anesthesia score ≥ 1 and ≤ 10 mm/5 min
2.02	Symptoms of DED at both the Screening and Baseline visits as defined by an OSDI total score of ≥ 13 with ≤ 3 responses of "not applicable (NA)".
2.03	BCVA of 20/100 or better in both eyes at the Screening visit
2.04	Good general and ocular health, as determined by the investigator using medical history, ophthalmic examination and history, physical examination, fasting blood chemistry and hematology, urinalysis, vital signs, and 12-lead ECG results at the Screening and Baseline visits, as applicable per the SoA (Section 1.3).
3.	Sex
3.01	Male or female

4.	Contraceptives	
4.01	Male participants willing to minimize the risk of inducing pregnancy for the duration of the clinical study	

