7.3. Lost to Follow-up

A participant will be considered lost to follow-up if they repeatedly fail to return for scheduled visits and are unable to be contacted by the study site.

The following actions must be taken if a participant fails to return to the clinic for a required study visit:

The site must attempt to contact the participant and reschedule the missed visit as soon as
possible and counsel the participant on the importance of maintaining the assigned visit
schedule and ascertain whether the participant wishes to and/or should continue in the
study.

[figure not shown]
Protocol 2012-201-005 Amendment 3

- Before a participant is deemed lost to follow-up, the investigator or designee must make
 every effort to regain contact with the participant (where possible, 3 telephone calls, and
 if necessary, a certified letter to the participant's last known mailing address or local
 equivalent methods). These contact attempts will be documented in the participant's
 medical record.
- Should the participant continue to be unreachable, he/she will be considered to have withdrawn from the study.
- Discontinuation of specific sites or of the study as a whole are handled as part of Appendix 1.

8. Study Assessments and Procedures

- Study procedures and their timing are summarized in the SoAs for Stage 1 (Table 1-1) and Stage 2 (Table 1-2). The overall study design is illustrated in Figure 1-1 (Stage 1) and Figure 1-2 (Stage 2). The visit schedule for Stage 1 includes 5 visits: Screening, Baseline (Day 1), Day 2, Day 8, and Day 15 (Exit). The visit schedule for Stage 2 includes 6 visits: Screening, Baseline (Day 1), Days 14, 28, and 42 (Exit). Unless otherwise specified, procedures must be performed in the order listed in the SoAs.
- Protocol waivers or exemptions are not allowed.
- Immediate safety concerns must be discussed with the sponsor immediately upon occurrence or awareness to determine if the participant must continue or discontinue study intervention.
- Adherence to the study design requirements, including those specified in the SoAs, is essential and required for study conduct.
- All screening evaluations must be completed and reviewed to confirm that potential
 participants meet all eligibility criteria. The investigator will maintain a screening log to
 record details of all participants screened and to confirm eligibility or record reasons for
 screening failure, as applicable.

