8.1.4. Dilated Fundus Exam

Biomicroscopic examination, indirect lenses, direct/indirect ophthalmoscopy, etc. are to be used as appropriate to visualize. Dilating drops should not be administered until slit lamp biomicroscopy and IOP measurements are completed.

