8.1.10. Other Assessments

Drop Tolerability Questionnaire

[figure not shown]
Participants will be asked to rate the acute overall tolerability attributes of study interventions on an 8-question visual analog scale (VAS) Drop Tolerability Questionnaire. Rating will commence $5 (\pm 1)$ minutes after the in-office eye drop administration. Participants will be instructed to mark a vertical line on the anchored VAS that best captures their experience with the study eye drops. This is an overall evaluation, not per eye. The questionnaire will include the following questions:

- How comfortable are the study eye drops in your eyes?
- How soothing are the study eye drops in your eyes?
- How moistening/lubricating are the study eye drops in your eyes?
- How clear is your vision with the study eye drops in your eyes?
- How much stickiness do you have with the study eye drops in your eyes?
- How much blur do you have with the study eye drops in your eyes?
- How much burning/stinging do you have with the study eye drops in your eyes?
- How much discomfort do you have with the study eye drops in your eyes?

Each question will be accompanied by the VAS scale. The assessment line length of the scale will be 100 mm and will be similar to the following depiction (Figure 8-1).

Figure 8-1 Drop Tolerability Questionnaire: Visual Analog Scale Assessment

How comfortable are the study eye drops in your eyes?

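### Read as written, Table 1-1 puts the Visit 5 dilated fundus exam before the predose tear sample, the dose and the Drop Tolerability Questionnaire, which may confound the Day 15 vision items and that tear value

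*Protocol*

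**What the plan says.** The header of Protocol Table 1-1 requires that procedures for a "timepoint must be performed in the order listed below" unless otherwise specified. Section 8 repeats the rule: "Unless otherwise specified, procedures must be performed in the order listed in the SoAs". Table 1-2 (Stage 2) marks some rows with a symbol that allows a flexible order; Table 1-1 has no such mark.

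The visible Table 1-1 rows run: slit lamp, "Intraocular pressure", "Dilated fundus exam", randomization, blood PK, tear PK, dosing, Drop Tolerability Questionnaire (DTQ). IOP is scheduled at Visits 1 to 5. The dilated exam is scheduled at Visits 1 and 5 (or Early Termination).

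Sections 8.1.3 and 8.1.4 place IOP after the slit lamp and dilation after both: "Dilating drops should not be administered until slit lamp biomicroscopy and IOP measurements are completed". Neither section ties IOP or dilation to the dose, the tear sample or the DTQ.

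Section 8.1.10 lists eight DTQ items. One asks how clear vision is; another asks "How much blur do you have with the study eye drops in your eyes". The Stage 1 SAP (Section 5.6.3.10 and Table 5-16) summarizes each item as raw values and as change from Day 1, by cohort and arm.

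On DTQ timing, Table 1-1 says "Drop Tolerability Questionnaire must be administered within approximately 5 minutes following morning administration of study intervention", while Section 8.1.10 starts the rating at 5 minutes, plus or minus 1.

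**The concern.** DTQ score and tear PK both belong to the primary objectives of Stage 1 (Protocol Section 3.1). If pupils are dilated before the Day 15 questionnaire, two of its items can register the dilation as well as the study drop. The planned summary subtracts an undilated Day 1 score, so the within-arm Day 15 change mixes the two. Drops given for dilation would also be in the eye before the Visit 5 predose tear sample but not before the Visit 3 one. Depending on the separate PK plan, which is not in these documents, the Visit 5 predose value may enter the steady-state minimum and serve as the first point of the AUC over the dosing interval.

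Table 1-2 lists IOP and the dilated exam after dosing and the DTQ. The two stages therefore use different orders, and no reason is given.

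**Working it through.** No power or sample-size figure is involved, so the check is a visit-by-visit reading of Table 1-1 followed by counts.

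**Step 1. What precedes what, taking the listed order literally**

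| Visit (day) | IOP before dose | Dilation before dose | Predose tear PK sample | DTQ |
|---|---|---|---|---|
| 2 (Day 1) | yes | no | no | yes |
| 3 (Day 2) | yes | no | yes | yes |
| 4 (Day 8) | yes | no | no | yes |
| 5 (Day 15) | yes | yes | yes | yes |

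Tonometry is common to all four dosing visits. Dilation is what sets Day 15 apart.

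**Step 2. Counts**

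- Arm sizes, reproducing the plan: 24 × 3/8 = 9 per active arm and 24 × 1/8 = 3 per vehicle arm, per cohort.
- DTQs after dilation: 1 of 4 per participant (25%). Per cohort, 24 of 24 × 4 = 96. Over two cohorts, 48 of 192; over three, if the optional Cohort 1C is run, 72 of 288.
- Per cohort and active arm: 9 of 36. Per vehicle arm: 3 of 12.
- DTQ items that ask about vision: 2 of 8.
- Predose tear PK samples after dilation: 1 of 2.

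**Step 3. How close dilation is to the questionnaire**

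Section 8.1.7 requires the Visit 5 predose ECG within 120 minutes before dosing, and the ECG row is listed above the dilated exam. If the order is kept throughout, dilation comes at most 120 minutes before the dose. It then comes at most about 120 + 5 = 125 minutes before the DTQ.

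**Step 4. Effect on the contrasts**

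Let *b* be a common shift from dilation on a vision item (100 mm scale). The documents give no value, so 5, 10 and 20 mm are assumed for illustration.

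- Within-arm change, Day 15 minus Day 1: (Day 15 score + *b*) − Day 1 score, shifted by *b* = 5, 10 or 20 mm.
- Within-arm change at Day 2 or Day 8: shifted by 0.
- A mean over the four visits, if one were taken: shifted by *b*/4 = 1.25, 2.5 or 5 mm.
- Active minus concurrent vehicle at Day 15: *b* − *b* = 0. This assumes an additive shift, no ceiling effect and no interaction with the drug.

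**Step 5. DTQ timing**

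The Table 1-1 note allows any moment up to about 5 minutes after the dose. Section 8.1.10 allows 5 − 1 = 4 to 5 + 1 = 6 minutes. The two overlap only from 4 to about 5 minutes.

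**The case against.** Row position is not a strict clock. The ECG and blood PK rows also sit above dosing, yet their notes extend to postdose times. The IOP and dilated exam rows carry no predose or postdose label, and the rule applies within a timepoint unless otherwise specified. A site could therefore have dilated later. That stands as an ambiguity, but nothing in the Stage 1 text specifies a later time, so the literal order is the default reading.

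Every cohort has concurrent vehicle arms on the same schedule, and undilated scores exist at Days 2 and 8. This stands, with the caution that each vehicle arm has only 3 participants per cohort and the planned summary is a within-arm change. The Day 15 versus Day 1 contrast is also imperfect for another reason: Day 1 dosing is to the left eye only, while the DTQ is not rated per eye. Reordering does not mend that.

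A reader might infer that anesthetic on Day 1 blunts stinging scores and adds a second contrast with Day 15. The documents do not carry that far. Criterion 2.01 in Section 5.1.1 does require a "Schirmer test with topical anesthesia score" in range at Screening and Baseline, but no such row is visible in Table 1-1. As an eligibility test it has to come before dosing. The documents name no agent for tonometry, which in any case is common to Visits 2 to 5.

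A reader might also want to copy the Table 1-2 order into Stage 1. That would put tonometry and dilation before or among the postdose tear samples (0.5 h at Visit 4; 0.5 to 12 h at Visits 3 and 5, Table 8-14). Stage 2 has a single postdose tear time and no serial profile, so it is not a precedent.

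**Conclusion.** The point holds in a limited form. As written, Visit 5 dilation precedes the predose tear sample, the dose and the DTQ. This possibly confounds the within-arm Day 15 change on the clarity and blur items, and the Visit 5 predose tear value relative to Visit 3. The size is unknown: the documents name no dilating agent, fix no direct interval and give no effect. The conclusion assumes that sites followed the listed order and that dilation persisted to the questionnaire.

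A reader might go further and say that the tolerability data are contaminated or that the Stage 2 dose choice is compromised. The documents do not support either. Three of four questionnaires are free of dilation, and a common additive shift leaves active versus vehicle unchanged. The DTQ is also one of nine listed safety and tolerability measures, and nothing shows that the dose turned on two vision items on Day 15.

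**What to change.** In Table 1-1, move only the Visit 5 dilated fundus exam to after the last (12 h) postdose tear sample, and say so in a note. Leave slit lamp and IOP where they are. This keeps the slit lamp, IOP, dilation sequence of Sections 8.1.3 and 8.1.4, and it keeps IOP predose as at baseline. Do not place tonometry or dilation between the dose and the postdose tear samples. Early Termination visits need no change, since Table 1-1 has no dosing, tear sampling or DTQ there. The cost is one row and one note, with no added procedure; the downside is an exam at the end of a long visit.

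The Stage 2 SAP (Section 10.0) says that Stage 1 is complete and its database lock has occurred, so for the existing data the remedy is in reporting. State the procedure order in force; the Stage 1 SAP is written on Amendment 2, while the schedule reviewed here is Amendment 3. Read the Day 15 clarity and blur scores against concurrent vehicle and against Days 2 and 8, and flag the Visit 5 predose tear value as taken after dilation if the listed order was followed.

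Separately, reconcile the DTQ timing in Table 1-1 with Section 8.1.10.
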